
Under the assumptions of a median survival of the control group of 8 months and a hazard ratio of 0.69, the required total sample size to achieve a 85% power to compare the experimental group (pooled DT 20mg/m² and DT 30mg/m² groups) versus BSC with a significance level of 2.5% one sided is 348 patients in the ITT population (116 patients in the BSC group and 232 patients in DT groups). It is expected that 10% of patients will be lost to follow-up; this leads to a calculated total sample size of 390 randomised patients.
 
Child Pugh A population (85% of the patient population):
 
Under the assumptions of a median survival of the control group of 9 months and a hazard ratio of 0.68, the required total sample size to achieve a 80% power to compare experimental group (pooled DT 20mg/m² and DT 30mg/m² groups) versus BSC with a significance level of 2.5% one sided is 291 patients in the ITT Child Pugh A population (97 patients in the BSC group and 194 patients in DT groups). It is expected that 10% of patients will be lost to follow-up; this requires for a calculated total sample size of 324 ITT Child Pugh A randomised patients.
 
Main efficacy analyses:
 
Results will be presented by treatment group and with all treatment groups pooled.
 
The primary endpoint is overall survival in the ITT population (all randomized patients). The 95% confidence intervals for hazard ratios and median times will be constructed and the Kaplan-Meier method will be used and plotted as curves by treatment group (pooled DT 20mg/m² and DT 30mg/m² groups) versus BSC group. The comparison between experimental group and BSC group will be made using the unstratified LogRank test. The analysis will be performed when 285 events have been observed.
 
The hierarchical sequential closed test procedure will be used to control the overall type I error rate of 5% to evaluate first the OS primary endpoint in the ITT overall population, then if statistically significant, the OS primary endpoint in ITT Child Pugh A population and then if statistically significant, the two main secondary endpoints (PFS and OOR) in the ITT Child Pugh A population.
 
To determine the optimal dose of DT between 20mg/m² or 30 mg/m², all statistical analyses (efficacy and safety) will be repeated as exploratory in the DT 20mg/m² group alone versus BSC and DT 30mg/m² group alone versus BSC. The dose of DT which presents the best benefit/risk ratio will be selected.
 
For secondary and exploratory endpoints, all time to event endpoints will be estimated using the Kaplan-Meier method and plotted as curves by treatment groups. The comparisons between DT groups and BSC will be made using LogRank tests. Proportion of subjects with objective response, disease control... will be compared between DT groups and BSC by the chi-square test. Estimates and 95% confidence intervals for the difference in proportions between DT groups and BSC will be provided. Estimate and confidence intervals for the odds-ratio will also be provided.
		

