9.4.3 Exploratory endpoints

No adjustment for multiple testing will be performed in the analysis of exploratory endpoints and p-values will be interpreted as exploratory.

All exploratory analyses will be conducted in ITT and ITT Child Pugh A population.

1. PFS by the Independent Radiological Review according to mRECIST is defined as the time from the date of randomisation to the date of the first documented progression or death from any cause. Patients without documented progression or death at the end of study treatment period will be censored at the date of their last tumour assessment.

PFS will be estimated by the Kaplan-Meier method and plotted as curves by treatment group. The comparison between groups (pooled DT 20mg/m² and 30mg/m² versus BSC) will be made using LogRank test.

2. PFS by the investigator according to RECIST 1.1 (and mRECIST if possible) is defined as the time from the date of randomisation to the date of the first progression (documented or clinical) or death from any cause. Patients without progression or death at the end of study treatment period will be censored at the date of their last tumour assessment.

PFS will be estimated by the Kaplan-Meier method and plotted as curves by treatment group. The comparison between groups (pooled DT 20mg/m² and 30mg/m² versus BSC) will be made using LogRank test.

3. ORR by the independent radiological review according to mRECIST is defined as the proportion of patients whose best overall response is complete or partial response during the study treatment period.

The comparison between groups (pooled DT 20mg/m² and 30mg/m² versus BSC) will be made using chi-square test .

4. ORR by the investigator according to RECIST 1.1 (and mRECIST if possible) is defined as the proportion of patients whose best overall response is complete or partial response during the study treatment period.

The comparison between groups (pooled DT 20mg/m² and 30mg/m² versus BSC) will be made using chi-square test.

5. Time To Progression (TTP):

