TTP is defined as the time from the date of randomisation to the date of the 1st documented progression or death related to tumour progression. The assessment of progression will be done by the independent radiological review according to RECIST 1.1 and mRECIST (if possible) and by the investigator according to RECIST 1.1 and mRECIST (if possible). Patients without progression at the end of study treatment period will be censored at the date of their last tumour assessment.

Definition of date of progression or censoring will refer to FDA guidelines for TTP.

TTP will be estimated by the Kaplan-Meier method and plotted as curves by treatment group. The comparison between groups (pooled DT 20mg/m² and 30mg/m² versus BSC) will be made using LogRank test.

6. Best Overall Response and Disease Control Rate:

The assessment of tumour response will be done by the Independent Radiological Review according to RECIST 1.1 and mRECIST (if possible) and by the investigator according to RECIST 1.1 and mRECIST (if possible).

Best Overall Response is defined as the best response observed during the study treatment period (no requirement for confirmation).

Disease Control Rate is defined as the proportion of patients whose Best Overall Response is complete response, partial response or stable disease during the study treatment period.

The comparison between groups (pooled DT 20mg/m² and 30mg/m² versus BSC) will be made using chi-square test.

7. Time to Objective Response:

Time to Objective Response will be calculated from randomisation to the date to first documented objective response (CR or PR). Patients without documented response (CR or PR) at the end of study treatment period will be censored at the date of their last tumour assessment. The assessment of tumour response will be done by the Independent Radiological Review according to RECIST 1.1 and mRECIST (if possible) and by the investigator according to RECIST 1.1 and mRECIST (if possible).

8. Duration of Response:

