Duration of response will be calculated in the subpopulation of patients experiencing a response (CR or PR) from the time when objective response (CR or PR) is first met to the date of first documented progression. The assessment of tumour response and progression will be done by the Independent Radiological Review according to RECIST 1.1 and mRECIST (if possible) and by the investigator according to RECIST 1.1 and mRECIST (if possible). Patients without documented progression at the end of study treatment period will be censored at the date of their last tumour assessment.

Duration of Response will be estimated only for patients achieving an objective response using the Kaplan-Meier method and plotted as curves by treatment group.

9. Evolution in serum α -foetoprotein levels (AFP):

Serum AFP levels will be summarized by visit and by dose. Differences between AFP levels every other month and at baseline will be summarized as well. Comparisons between groups will also be made using non parametric tests. The number of patients with a decrease in AFP from baseline will be shown overall and by dose of DT.

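### Duration of response censors responders who die, so its Kaplan-Meier estimate overstates the time patients remain alive and in response

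*Combined protocol and SAP*

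**What the plan says.** Duration of response (section 9.4.3, item 8) runs "from the time when objective response (CR or PR) is first met to the date of first documented progression". The censoring rule is "Patients without documented progression at the end of study treatment period will be censored at the date of their last tumour assessment", and the estimator is stated: "Duration of Response will be estimated only for patients achieving an objective response using the Kaplan-Meier method". Death is not mentioned.

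Time to objective response (item 7) runs from randomisation to first CR or PR, with the rule "Patients without documented response (CR or PR) at the end of study treatment period will be censored at the date of their last tumour assessment". Item 7 names no estimator, but the synopsis says "For secondary and exploratory endpoints, all time to event endpoints will be estimated using the Kaplan-Meier method".

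Elsewhere in the plan death is handled explicitly. PFS ends at "the date of the first documented progression or death from any cause" (section 9.4.3 item 1, and the same in section 9.4.2). TTP (item 5) counts a death if it is attributed to the tumour. The plan refers to FDA guidelines for event and censoring dates for OS, PFS and TTP, but not for items 7 and 8.

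**The concern.** A responder who dies without a documented progression is censored at the last scan. Kaplan-Meier assumes that a censored patient has the same future as those still under observation. A patient who has died is no longer responding, so that assumption fails, and the curve reads as if death had not ended the response.

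The same reasoning applies to time to response. A patient who dies or progresses first is censored, as if a response could still come.

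What is at stake is the accuracy of two descriptive summaries. Duration of response is to be plotted by treatment group, and section 9.6 repeats the efficacy analyses for each dose against BSC. A reader will take the median as the time patients stay in response.

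**Working it through.** The documents state no figure for either endpoint, so there is nothing to reproduce. The check is a comparison of definitions followed by an illustration on assumed values.

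**1. Definitions side by side**

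| Endpoint | Deaths counted as events |
|---|---|
| PFS (9.4.2; 9.4.3 items 1–2) | Any cause |
| TTP (9.4.3 item 5) | Tumour-related only |
| Duration of response (9.4.3 item 8) | None |

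A responder who dies of the tumour before a scan shows progression is an event for PFS and for TTP, but is censored for duration of response. The duration rule is therefore looser than TTP and cannot be explained as a TTP-type definition.

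**2. Duration of response, constant hazards**

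Let h be the progression hazard among responders, and f·h the hazard of death without documented progression.

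- Median under the plan's rule: ln 2 / h.
- Median to progression or death: ln 2 / [h(1 + f)], which is the reported median divided by (1 + f).

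For an assumed reported median of 4.0 months:

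| Assumed f | Death-inclusive median (months) | Reported median too long by |
|---|---|---|
| 0.10 | 4.0/1.10 = 3.64 | 10% |
| 0.33 | 4.0/1.33 = 3.01 | 33% |
| 0.50 | 4.0/1.50 = 2.67 | 50% |

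Equivalently, if q = f/(1 + f) is the share of responders whose first event is death, the inflation factor is 1/(1 − q): 1.11, 1.25 and 1.43 at q of 10%, 20% and 30%.

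**3. Check with 2-monthly scans**

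Section 3 sets scans every 2 months. A simulation of 4,000 responders used an assumed median of 6 months to progression or death, detected progression only at scans, and censored deaths at the last scan. Estimated probability of still being in response:

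| q | Month 6: plan's rule / death as event | Month 12: plan's rule / death as event |
|---|---|---|
| 10% | 0.542 / 0.506 | 0.293 / 0.256 |
| 20% | 0.580 / 0.504 | 0.321 / 0.243 |
| 30% | 0.608 / 0.497 | 0.373 / 0.246 |

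The direction is the same throughout, and the gap widens with q.

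**4. Time to response**

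Assume a median of 4 months to response or competing exit (λ = ln 2/4 per month) and an eventual response proportion p.

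- Cumulative incidence: p(1 − e^(−λt)).
- One minus Kaplan-Meier: 1 − e^(−pλt).

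At 12 months λt = 2.079:

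| Assumed p | Cumulative incidence | 1 − Kaplan-Meier |
|---|---|---|
| 5% | 4.4% | 9.9% |
| 10% | 8.8% | 18.8% |
| 20% | 17.5% | 34.0% |

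On these assumptions Kaplan-Meier roughly doubles the apparent probability of response.

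**The case against.** **Little depends on these endpoints.** This stands. Both are exploratory, outside the OS, PFS and ORR testing sequence. The dose-selection rule in section 9.6 uses OS, then treatment discontinuations and deaths due to adverse drug reactions. Fatal toxicity is counted in OS and in the safety comparison, so the duration rule does not hide it.

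**Progression-only duration is a legitimate cause-specific quantity.** This stands in part. It can describe how quickly responders progress, but it is not the time patients spend alive and in response, which is how a median duration is read. The plan gives no reason for counting fewer deaths here than in TTP.

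**Kaplan-Meier for time to response is an inference.** This also stands in part. It comes from the synopsis's general sentence, not from item 7. A summary in responders only would be free of the problem, but item 7's censoring rule for non-responders would then have no purpose. ORR is also reported as a plain proportion, so readers have a correct figure beside it.

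**Other text might settle it.** Section 5.3 is redacted, and section 9.1.1 announces a separate SAP. Either could add a rule. Nothing in the readable text does, and item 8's wording is explicit.

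**A stronger reading that the documents do not support.** A reader might infer that the error favours DT, because DT has caused fatal lung toxicity. The five ARDS cases in section 7.6.1, two of them fatal, followed intra-arterial injection over 15–30 minutes; this trial infuses intravenously over 6 hours with preventive measures. Section 7.5 does list serious respiratory events and death in previous studies, so the risk is not excluded. But what matters is the rate of death without documented progression among responders in each arm, and no such rate is given. BSC responders may also die without a progression scan. The between-arm direction is unknown.

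**Conclusion.** The point holds as a minor one. As written, the duration-of-response estimate overstates time alive and in response, and its treatment of death is inconsistent with both PFS and TTP. Under constant hazards the overstatement of the median equals f, so 10%, 33% or 50% at f of 0.10, 0.33 or 0.50. These values show sensitivity; they do not predict the bias in this trial, because f, the medians and the response proportions are all assumed.

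The time-to-response point is secondary and conditional on the synopsis's Kaplan-Meier rule being applied to it. Exploratory status justifies leaving out multiplicity control, but it does not make either estimate accurate.

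**What to change.** - **Duration of response:** define it as first CR or PR to first documented progression or death from any cause, whichever comes first, with the same event and censoring window as PFS. The PFS and duration rules both refer to the end of the study treatment period, so state once, for both, whether progressions and deaths after treatment stops count. Adding death alone would leave that window open.
- **Time to response:** report cumulative incidence with death and progression as competing events, or describe the times in responders only and drop the censoring rule.

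The cost is a few sentences in the SAP. No new data are needed, since sections 3 and 4.4 already require survival status for all patients, including those withdrawn. The downside is a shorter reported duration of response.

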9.5 Safety endpoints

Safety analyses will be descriptive and conducted in the safety population.

Descriptive data will be provided for adverse events, laboratory values (biochemistry and hematology), vital signs (weight, blood pressure), clinical exams (normal/abnormal), and concomitant treatments.

Patients with at least one AE, SAE, severe AE, AE leading to discontinuation, AE leading to dose reduction, and AEs of interest will be summarized. Adverse events will be coded using MedDRA.

Respiratory:

- Incidence and duration of reduction of SaO₂ during DT infusion (in DT arms);
- Incidence and severity of respiratory events;

Cardiac:

- Incidence and severity of cardiovascular events (including BP and HR);
- ECG and LVEF change ;

Overall:

- Incidence and severity of all TEAEs and SAEs according to NCI-CTC v4.0 scale;
- Biological (haematology and biochemistry analyses and particularly AST/ALT, WBC);
- Child Pugh Score deterioration.

Safety endpoints will be individually described per subject number, presenting: emergence, description, body system, preferred term, date and time of onset, date and time of last study

drug administration before AE, time from onset since last study drug administration, frequency, severity and seriousness, relationship to study drug, action taken (corrective treatment, hospitalisation...) required and outcome if any.

The treatment emergent AEs (TEAEs), defined as those events that occurred or worsened after the first drug administration, will be summarized by body system and preferred term. The number of emergent AEs and the number of subjects reporting these emergent AEs will be presented by treatment group and overall.

The same table presentation will be used for serious TEAEs, drug related TEAEs and drug related serious TEAEs.

9.6 Determination of the optimal dose of DT

The statistical analyses comparing the experimental group (pooled DT 20mg/m² and 30mg/m² groups) versus BSC will also be conducted in the DT 20mg/m² group alone vs BSC and DT 30mg/m² group alone vs BSC in the ITT population.

Baseline demographic characteristics, exposure, efficacy, safety and adjustment for covariates (as described in Sections 9.3, 9.4 and 9.5 of the protocol) will be compared for each DT group versus BSC (as exploratory analysis).

The selection of the optimal DT dose will be based on the benefit/risk ratio of each dose of DT, taking into account:

- **Benefit/Efficacy:** The optimal dose of DT in term of efficacy will be the one which is associated with the best survival in comparison with the BSC group.

This will be assessed through the measure of OS and tested by the unstratified log-rank test.

The optimal dose for efficacy will be identified if one out of the 2 exploratory unstratified log-rank tests between the DT 30 mg/m² versus BSC or DT 20 mg/m² group versus BSC is statistically significant or if a clinically relevant difference is observed in favour of one DT group versus BSC (i.e. unstratified log-rank tests between the DT 30 mg/m² versus BSC or DT 20 mg/m² group versus BSC less than 15%).

If there is no difference between the DT 30mg/m² versus BSC and DT 20mg/m² group versus BSC (i.e. unstratified log-rank tests between the DT 30 mg/m² versus BSC or DT 20 mg/m² group versus BSC more than 15%), it will be concluded that DT 20 mg/m² and DT 30 mg/m² are similar in term of efficacy.

- **Risk/Safety:** The optimal dose of DT in term of safety will be the one which is associated with the lowest incidence of treatment discontinuations due to adverse drug reactions and the lowest incidence of deaths due to adverse drug reactions.

Difference between the two doses of DT (DT 30 mg/m² versus DT 20 mg/m²) will be explored via two-sided Fisher exact tests on the incidence of treatment discontinuations and on the incidence of death due to adverse drug reactions.

If at least one exploratory Fisher test leads to conclude to a statistically significant difference between the DT 30 mg/m² group and the DT 20 mg/m² group, or if a clinically

relevant difference is observed between groups (absolute difference of more than 5%), the optimal dose of DT for safety will be the one which is associated with the lowest incidence of study treatment interruptions or deaths due to adverse drug reactions. If there is no difference between the dose groups for these safety criteria, it will be concluded that DT 20 mg/m² and DT 30 mg/m² are similar in term of safety.

In summary, the optimal DT dose will be the dose of DT associated with the best OS (if any). If OS is similar between the 2 doses of DT, the optimal DT dose will be the one associated with the best tolerance. If OS and safety are found to be comparable between doses, then the lowest dose (20mg/m²) will be selected.

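### The dose-selection rule in section 9.6 infers OS similarity between the DT doses from separate p-values versus BSC, contradicts itself when exactly one is below 15%, and is incomplete when both are

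*Combined protocol and SAP*

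**What the plan says.** Determining the optimal dose is a secondary objective (section 2.2). Section 9.6 repeats the pooled analyses for each dose against BSC. The optimal dose for efficacy "will be the one which is associated with the best survival in comparison with the BSC group".

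Two sentences put this into operation:
- "The optimal dose for efficacy will be identified if one out of the 2 exploratory unstratified log-rank tests" versus BSC is significant, or if a "clinically relevant difference is observed in favour of one DT group versus BSC". The second condition is explained as a log-rank p-value for DT 30 or DT 20 below 15%.
- The next sentence takes p-values for DT 30 or DT 20 "versus BSC more than 15%), it will be concluded that DT 20 mg/m² and DT 30 mg/m² are similar in term of efficacy".

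Safety is handled differently: "Difference between the two doses of DT (DT 30 mg/m² versus DT 20 mg/m²) will be explored via two-sided Fisher exact tests", with an absolute difference of more than 5% counted as clinically relevant. The summary then orders the steps. The dose with the best OS is chosen, if there is one. "If OS is similar between the 2 doses of DT, the optimal DT dose will be the one associated with the best tolerance". If both OS and safety are comparable, the lower dose is taken.

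Section 9.1.3 states that the study is not comparative between the two doses. It describes the by-dose step as an exploratory comparison of confidence intervals versus BSC, and refers to 9.6.

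**The concern.** Three separate faults sit in the efficacy step.

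1. **Invalid inference.** Two p-values versus BSC above 15% say that neither dose has been shown to differ from BSC. They carry no conclusion about one dose against the other. No DT 30 versus DT 20 OS estimate is planned, although the same section compares the doses directly for safety.
2. **Contradiction.** Both sentences join the two tests with an *or*. If exactly one p-value is below 15%, the first sentence identifies a dose and the second calls the doses similar. *Both above 15%* is probably what was meant, but the text does not say it.
3. **Gap.** If both p-values are below 15%, the text offers best survival as a principle but names no measure (HR, median, p-value) and gives no criterion for similar OS. It is then undefined when selection passes to tolerance.

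At stake is whether the stated secondary objective can be answered by a rule fixed in advance, or only by a choice made after the data are seen.

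**Working it through.** **Inputs from the documents.** 285 deaths at analysis, pooled HR 0.69, 85% power (section 9.1.2); 1:1:1 randomisation (section 3); 130 patients per group (Synopsis); cuts of 5% and 15% (section 9.6).

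**Assumptions.** 285/3 = 95 deaths per arm; normal approximation to the log HR. The documents give no HR by dose, so pairs whose geometric mean is about 0.69 are used: 0.69/0.69, 0.60/0.78 (0.68) and 0.58/0.82 (0.69).

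**The plan's own figure.** Schoenfeld power for pooled DT versus BSC: sqrt(285 × 1/3 × 2/3) × |ln 0.69| − 1.96 = 7.96 × 0.371 − 1.96 = 0.99, so power is 84% against 85% stated. The event count is a sound base.

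**Standard errors.** Any two single arms: sqrt(2/95) = 0.145. Pooled DT versus BSC: sqrt(1/190 + 1/95) = 0.126. An observed HR versus BSC of 0.81 gives p = 15%, and 0.75 gives p = 5%.

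**Does the inference hold?** Two possible results:

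| Observed HRs versus BSC | p versus BSC | 9.6 outcome | Dose-to-dose HR (95% CI) | Pooled p |
|---|---|---|---|---|
| 0.82 and 1.20 | 0.17, 0.21 | similar | 0.82/1.20 = 0.68 (0.51–0.91), p = 0.009 | 0.95 |
| 0.80 and 0.82 | 0.12, 0.17 | dose named by one sentence, similar by the other | 0.80/0.82 = 0.98 (0.73–1.30), p = 0.86 | 0.093 |

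The first calls clearly different results similar. The second separates nearly identical results. Both are trials that fail the primary test.

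**Can both p-values exceed 15% in a successful trial?** With equal deaths per arm, pooled Z = (Z20 + Z30)/sqrt(3). If both |Z| are below 1.44, pooled |Z| is at most 2 × 1.44/1.732 = 1.66, p = 0.096. So no.

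**How often does each case arise?** 4 million draws with a shared BSC arm; a p-value counts as below 15% only in favour of DT:

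| Assumed HRs | All trials: both / one / neither below 15% | Positive pooled test: both | Positive pooled test: exactly one |
|---|---|---|---|
| 0.69/0.69 | 78 / 17 / 5% | 92% | 8% |
| 0.60/0.78 | 60 / 38 / 2% | 70% | 30% |
| 0.58/0.82 | 47 / 52 / 1% | 56% | 44% |

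Under these assumptions every successful trial lands either in the gap (both) or in the sentence pair that conflicts as written (exactly one). If a single p < 5% is allowed to name the dose when both are below 15%, the unresolved share of successful trials falls to 72%, 47% and 33%.

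A three-arm log-rank simulation (130 per arm, control median 8 months; uniform accrual over 57 months and 10% loss assumed; 6,000 runs) gave 80%, 62% and 49% for both below 15% in all trials. It gave no run with a positive pooled test and neither below 15%, and about 184 DT deaths.

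**What a direct comparison could show.** With 190 DT deaths the 95% CI factor is exp(1.96 × 2/sqrt(190)) = 1.33, so an estimate of 1.0 has a CI of about 0.75 to 1.33.

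**The case against.** The strongest reply is that the damage is limited where the rule matters. The invalid similarity conclusion, read as both p-values above 15%, cannot arise once pooled DT has beaten BSC, and both worked examples are failed trials. In positive trials with exactly one dose below 15%, that dose is the truly better one in 99.8% of cases at 0.60/0.78 and 96% at 0.69/0.80. With both below 15%, the better OS estimate picks the better dose in about 95% and 80%. This stands. It does not supply the missing rule: no text says that the better estimate is what ranks the doses. If it were, the doses would essentially never tie and tolerance would not be reached. At 0.69/0.69 the better estimate is a coin toss, and only 3% of the both-below-15% trials have a direct comparison with p < 0.05.

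A reader might infer that the plan defines neither best nor similar at all. The documents do not support that: section 9.6 gives a 15% cut. The cut is invalid for comparing doses and incomplete; it is not absent.

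Nor is it right that by-dose intervals are missing. Section 9.4.1 specifies HRs and 95% CIs, and 9.6 repeats the analyses by dose. They are simply not used in the decision, so 9.1.3 and 9.6 need aligning.

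Finally, not comparing the doses is a declared choice, the by-dose work is exploratory, and section 9.1.1 leaves further detail to a separate SAP. That lowers the stakes. It does not license 9.6 to conclude that one dose is similar to the other and then use that conclusion to select.

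**Conclusion.** The concern holds for the dose-selection step only, and should be fixed. The rule in 9.6 is invalid for comparing doses, contradicts itself when exactly one p-value is below 15%, and leaves the both-below-15% case undefined. That last gap is the main one in a successful trial: 92%, 70% or 56% of trials with a positive pooled test at the three assumed HR pairs. These shares rest on 95 deaths per arm, a normal approximation and by-dose HRs that the documents do not give.

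A reader might go further and infer that a successful trial would declare clearly different doses similar. On the both-above-15% reading it cannot; only the literal *or* would allow it, and that is probably unintended. Nor is anything confirmatory affected: the primary test, the hierarchy and its alpha stand. No view is taken on which dose should be chosen.

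**What to change.** In section 9.6:
- Add an exploratory direct DT 30 versus DT 20 OS comparison (HR with 95% CI) in the 260 randomised DT patients. Base the efficacy step on it, with each dose versus BSC as support.
- Replace the conclusion of similarity with a statement that no difference was shown.
- Correct the *or* so that each combination of p-values leads to one outcome.
- Before database lock, state which OS measure ranks the doses and which estimate or interval sends selection to tolerance, including when both p-values versus BSC are below 15%.

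Reconcile section 9.1.3 (not comparative between doses; comparison of confidence intervals) with 9.6 (p-value cuts; conclusions about one dose against the other). As a drafting point only, the safety criterion begins as treatment discontinuations and ends as "lowest incidence of study treatment interruptions or deaths due to adverse drug reactions"; the two should match.

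**Cost.** Wording in 9.1.3, 9.6 and the SAP, and one extra Cox/log-rank run. No patients, no new data, no confirmatory alpha.

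**Downside.** About 184 to 190 DT deaths give a CI of roughly 0.75 to 1.33 around 1.0, so equality of the doses cannot be shown. A bare p > 15% on the direct test must not define similarity either: it would miss a true difference in about 36% of trials at 0.60/0.78 and 66% at 0.69/0.80.
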